 - Best corrected contrast sensitivity (CSV 1000)
 - Intraocular pressure, nondilated slit-lamp exam
 - Dark adaptation (AdaptDX, extended exam)
 - Macular pigment optical density (MapcatSF)
 - Macular ocular coherence tomography (Zeiss Cirrus OCT)
 - Fundus photography (Zeiss VisuCam Pro)

Because these patients will have additional problems found in routine clinical practice, other exams may occur for other problems and will not be considered part of the study data. Should any adverse effects be noted thought to be from the study treatment, the patient will be examined to understand the effect and if it is felt to be not significant, the patient will be asked to continue in the study. In the highly unlikely event a serious adverse effect is noted the patient will be terminated from the study and appropriate treatment will be undertaken.

DATA COLLECTION:

The data will be maintained on standardized forms and printable graphics, as well as in the patient's routine clinical file. To protect identifiable information, files will be locked in a file cabinet, accessible only the PI and the study coordinator. Data will be transcribed without

personally identifiable information into standard Excel files and analyzed as appropriate using standard statistical techniques.

STUDY REQUIREMENTS:

This study will be conducted with the protocol, good clinical practices and applicable regulatory requirements. This is a no significant risk study, using commercially available supplements, Lumega-Z or AREDS2, containing 2 or 3 of the three carotenoids that are FDA “generally recognized as safe” for food supplementation and are found in all healthy retinas. All examinations are noninvasive and are performed with FDA cleared, commercially available medical devices in routine clinical use.

The study population consists of 90 male and female patients in a routine clinical practice age 60 and over who have early macular degeneration as defined as a few drusen visible on Visucam and have an AdaptDx score less than or equal to 10 minutes. No vulnerable populations will be studied.

The patient will be studied for improvements in ocular function. Primary endpoints would be improvement in macular pigment optical density long form, improvement in best corrected contrast sensitivity and improvement in best corrected vision. Secondary endpoints would be improvement of AdaptDx long form time or a reduction in drusen.

The study supplements for each

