study subject will be kept in a locked cabinet until dispensed by study staff not involved with testing to the subject.

A protocol deviation log and an adverse effect log will be kept for each subject. Immediate attention will be paid to any serious adverse events, which by the nature of the study are completely unexpected. If any injuries occur to subjects in the protocol , they are considered to be under treatment for early AMD, (diagnosis AMD, ICD H35.3131) and will be dealt with as any other medical condition or complication of treatment.

Data will be reviewed for safety and unexpected positive or negative effects after three and six month visit period are completed for all subjects.

Data will be collected in the subjects routine electronic medical record and confirmed as complete on a hard copy visit log in a study folder for each subject. Copies of each visit will be kept in the study folder. There will be a protocol deviation log, adverse events log and a study supplement log in each subjects folder.

The information collected will be used in anonymous group data analysis to be prepared for submission for potential publication. The information will not be sold or used in future research. The data can be verified through the audit trail in the subject's individual electronic medical record original source. No data will be stored on a portable device. The data will not be destroyed because it is part of medical record of care of AMD unspecified for an individual and is subject to the laws of the state of Texas and the rules of the state medical board.

[name] • P: [contact] • F: [contact] • [contact]

If you require assistance answering any of the questions on this form,
please contact the Salus IRB at the number listed above.

Sponsor: Guardian Health Sciences, Inc

Protocol #: LungeaZ#1

JT 31Oct 17

A. ADMINISTRATIVE INFORMATION:

How did you learn of Salus IRB?

We are an existing client of Salus IRB Sponsor/CRO recommendation Tradeshow
 Industry Publication Internet/Website
 Other:

Sponsor Contact Information:

1.	Name of sponsor contact:	[name]
2.	Sponsor name:	Guardian Health Sciences, Inc
3.	[contact]
4.	Email:	[contact]

Provide the Primary Contact Information for IRB inquiries:

5.	Primary contact:	 Sponsor  CRO  Other: PI
6.	Name of primary contact:	[name]
7.	Name of company:	Eye Clinic of Austin

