3.	
Drug/Device Storage and Handling:  N/A – this study does not involve any drug or device
 
If the study involves drug(s) or device(s), which of the following measures will be followed? Check all that apply for each section.
 
a.  All drugs/devices will be stored appropriately in a secure area  pharmacy or central area  locked storage unit, cabinet or office  Other:
 
b.  Access to the drugs/devices will be limited to authorized research personnel  use of log indicating authorized personnel for controlled access  Other:
 
c.  Accountability records will be adequately recorded and maintained
 
d.  Who is responsible for dispensing the drug/device?  PI  Pharmacy personnel  Other: study coordinator
 
When appropriate, describe additional plans for the secure storage, handling and dispensing of drug(s) or device(s):

Sciences Inc.

SPONSOR: Guardion Health

PROTOCOL #: ~~Lumegaz Protocol 1~~

INVESTIGATOR: [name]

JT 31Oct17

L. DATA PROTECTIONS AND CONFIDENTIALITY:

1.	Will eConsent be utilized for this research? If yes, please provide a written statement or SOP confirming the eConsent process is Part 11 compliant.	 No  Yes
2.	Sensitive Information: Information which may upset the individual being asked about the information, or that if misused, could reasonably cause discrimination or stigmatism, and result in damage to the individual's financial well-being, employability, insurability, or reputation.	 No  Yes
3.	Will sensitive or individually identifiable health information, including demographic information, be collected using web-based tools, email, online surveys, etc.? If yes, the website or online tool should clearly explain how the information might be used and what measures will be taken to ensure confidentiality of their data.	 No (skip to section M)  Yes
	Attach the text version of the online tool for IRB approval.	

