Ingredients: Alaska Walleye Pollock (*theragra chalcogramma*), gelatin, glycerin, purified water, mixed natural tocopherols.

NO gluten, dairy, or artificial colors or flavors.

Each 4-week supply includes:

4 bottles x 5.25 Fl. Oz.

Lumega-Z Medical Food

With 60 Omega Boost Soft Gels

LUMEGA-Z®
Advanced Ocular Health
Medical Food

The Medical Food created
to restore and maintain the
Macular Pigment

LUMEGA-Z®
Advanced Ocular Health
Medical Food

Contains all three
macular carotenoids:

Lutein

Zeaxanthin

Meso-zeaxanthin

as well as a robust complex
of critical Micronutrients and
Omega 3's

GUARDION®
HEALTH SCIENCES
The Macular Pigment Specialists

Formulated and distributed by:
Guardion Health Sciences, Inc.
San Diego, California

[figure not shown]
Made in the U.S.A.

Patent Pending

[figure not shown]
What is Lumega-Z?

Lumega-Z is a medical food created to restore and maintain the macular protective pigment.

Macular pigment protects the macula (the part of your retina responsible for sharp, central vision) against oxidative stress, free radicals, and damaging blue light.

Example of a depleted macular pigment

[figure not shown]

Example of a restored macular pigment

A depleted macular pigment is a known high risk factor for age-related macular degeneration and other retinal diseases.

[figure not shown]
What is Medical Food?

A Medical Food is not a drug. It is not a supplement either.

Medical foods are a regulated category of product "... formulated to be consumed or administered... under the supervision of a professional healthcare provider and intended for the specific dietary management of a disease or condition for which distinctive nutritional requirements, based on recognized scientific principles, are established by medical evaluation."

(Per Section 5(b) of the Orphan Drug Act)

LUMEGA-Z®
Advanced Ocular Health
Medical Food

Restores and maintains a depleted macular pigment

Decreases glare and light sensitivity

Liquid formula is easy to swallow and digest

Promotes overall ocular health

Can replace your daily multivitamin

Able to be purchased with Healthcare Flexible Spending Account (FSA)

Tax-deductible as a medical expense

All research and scientific data is available upon request.

PreserVision AREDS 2 Formula Eye Vitamins for AMD

[name]

Thu 10/26/2017 11:32 PM

To: [name] <[contact]>;

[figure not shown]
Cc: [name] <[contact]>;

Sunday, October 15, 2017
4:26 PM

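### Having non-testing staff dispense the product does not by itself keep testers or the drusen reader unaware of arm, so at least acuity, contrast sensitivity and drusen change are open to bias towards Lumega-Z

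*Combined protocol and SAP*

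**What the plan says.** **Dispensing.** Protocol, STUDY REQUIREMENTS: supplements for each "study subject will be kept in a locked cabinet until dispensed by study staff not involved with testing to the subject". The site's IRB form (section K, item 3) names the dispenser: "Other: study coordinator".

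**Products.** STUDY REQUIREMENTS describes the trial as "using commercially available supplements, Lumega-Z or AREDS2". The attached product sheet shows Lumega-Z as a branded liquid ("Liquid formula is easy to swallow and digest") supplied with soft gels. The comparator is identified as a named commercial AREDS2 product. No dummy, over-labelling or matched packaging is described.

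**Visits.** The examination list under STUDY puts history first at baseline, 3 and 6 months. Acuity, contrast sensitivity, dark adaptation, macular pigment optical density (MPOD) and fundus photography come later in the list.

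**Records.** STUDY REQUIREMENTS: "Data will be collected in the subjects routine electronic medical record and confirmed as complete on a hard copy visit log" in the study folder, which also holds copies of each visit. On the logs: "There will be a protocol deviation log, adverse events log and a study supplement log in each subjects folder". Under DATA COLLECTION, "files will be locked in a file cabinet, accessible only the PI and the study coordinator".

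**Endpoints.** The primary endpoints are improvement in MPOD, best corrected contrast sensitivity and best corrected vision. "Secondary endpoints would be improvement of AdaptDx long form time or a reduction in drusen". No drusen reader, grading scale or masked reading is given.

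**Analysis.** The statistical analysis text sends data to outside analysts with only ID, age and sex as identifiers. It lists a possible mixed-design ANOVA with paired t-tests.

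**The concern.** Separating dispensing from testing has an evident purpose, which is to keep the person who tests from knowing the arm. The rest of the plan does not carry that purpose through, and the patient can undo it in one sentence during the history.

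The direction of any resulting bias is not neutral. The BACKGROUND section says the study will try to show an effect of the medical food greater than that of AREDS2. Acuity and contrast sensitivity depend on the patient's responses and can depend on how the tester prompts. Judging that drusen have been reduced needs a reader. If testers or readers know the arm, a difference favouring Lumega-Z can appear when the products are equal. None of the listed analyses could separate that difference from a product effect, so the protection has to be in place before data are collected.

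**Working it through.** **1. Who could learn the arm, reading the plan as written**

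| Person | What the documents say | Result |
|---|---|---|
| Patient | Two commercial products, one a branded liquid kit; no dummy or matched packaging | Not masked |
| Tester | Does not dispense. History precedes testing in the visit list; no instruction against naming the product | Not secured |
| Investigator | May open the locked files; the supplement log is in the same folder as the visit copies; is the data and safety monitor (IRB submission form) | Can see the arm |
| Drusen reader | Not identified; no masked reading | Not secured |
| Outside analysts | Personal identifiers removed; coding of the arms not mentioned | Not stated |

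**2. What an assessment bias would do**

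The plan gives no power, effect size, SD or alpha, so it has no figure of its own to reproduce. The calculation below is an illustration.

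Inputs from the documents: 90 patients, randomised 2:1. Taking all 90 as randomised gives 60 on Lumega-Z and 30 on AREDS2.

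Assumptions: a two-sample t-test at two-sided 0.05, no true difference, and a spurious shift of d SD of change towards Lumega-Z. The values of d are assumed.

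- Standard error in SD units: √(1/60 + 1/30) = 0.2236
- Degrees of freedom: 60 + 30 − 2 = 88; critical value 1.987
- Noncentrality: d / 0.2236
- Chance of a false Lumega-Z win: P(noncentral t > 1.987)

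| Assumed shift d | Noncentrality | 60:30 | 40:20 |
|---|---|---|---|
| 0 | 0 | 2.5% | 2.5% |
| 0.1 SD | 0.447 | 6.5% | 5.5% |
| 0.2 SD | 0.894 | 14.1% | 10.7% |
| 0.3 SD | 1.342 | 26.3% | 18.9% |

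The noncentrality column is for 60:30. The 40:20 column covers the case where 30 of the 90 are the untreated normal group: standard error √(1/40 + 1/20) = 0.2739, 58 degrees of freedom, critical value 2.002. A normal approximation at 60:30 gives 6.5%, 14.3% and 26.8%, so the method hardly matters.

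These rates are per endpoint, and there are three primary endpoints.

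**The case against.** The strongest reply is that the plan has real controls. The files are locked and open only to the investigator and coordinator, so a tester who is neither cannot read the supplement log. The site form limits product access to authorised personnel and requires an access log. Analysis is done outside the site. All of this stands. It narrows the routes, but leaves the patient's own account during the history and the unmasked drusen reading.

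Several stronger readings are tempting, and the documents do not support them:

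- **The electronic record reveals the product.** The protocol puts outcome data there and the supplement log in the study folder. It does not say that the allocated product is entered in the record.
- **All three primary endpoints depend on effort or judgement.** The plan names the MPOD device but not how it measures, so the claim is limited to acuity and contrast sensitivity.
- **The investigator tests patients or reads drusen.** Neither is stated.
- **The sponsor's leaflet primes participants.** No page says they receive it, and the sponsor and site forms both answer No on study materials. Support for the direction of bias is the stated hypothesis.
- **The two products look different.** The AREDS2 dosage form is not in the supplied text. The point rests on openly supplied commercial products and the absence of any dummy.

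Two further objections hold in part. The shift sizes have no source in the documents, and the calculation uses one t-test although the analysis text mentions a mixed ANOVA. Masking testers also cannot remove bias that comes from patients who know their product. Both limit what the numbers can be used for, but neither closes the gap in the procedure.

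**Conclusion.** The point holds in limited form. The supplied text specifies no masking of patients, testers or drusen reader, and the dispensing split alone does not secure it. At least acuity, contrast sensitivity and drusen reduction are open to bias in the Lumega-Z versus AREDS2 comparison.

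The size is unknown. Under the assumptions above, a shift of 0.1 to 0.3 SD would take the false-win rate per endpoint from 2.5% to between about 6.5% and 26% at 60:30, or between about 5.5% and 19% at 40:20. Masked testing would remove only the part of any shift that comes from testers.

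Confidence is medium. Consent and other pages are missing from the supplied text, so masking described only there cannot be ruled out. Even then, it should be stated among the protocol's own procedures.

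**What to change.** Add to STUDY REQUIREMENTS:

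1. Keep the supplement log and the allocation list out of the subject folder, in a separate file held by the dispenser, with access whenever safety requires it.
2. Run acuity, contrast sensitivity, MPOD and AdaptDx with a fixed script before the history or any talk of the product. Tell patients not to name their product to testers. Adverse-effect assessment stays as the protocol has it, but takes place after testing.
3. Have whoever grades drusen work from coded photographs, with arm and visit order hidden.
4. Send data to the outside analysts with the two randomised arms coded A and B until the analysis is locked.
5. State that patients are not masked, as a limit on conclusions about acuity and contrast sensitivity.

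The cost is protocol wording, a re-ordered visit, coding of photographs and a separate file. The steps should need no extra staff, since dispensing and testing are already split. The exception to check is the drusen reader, whom the plan does not identify: if the investigator, who also monitors safety and data, is to grade drusen, hiding the arm will take more care.

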5.	Therapeutic area/indication:	 Respiratory  Hypertension  Cardiovascular/Cardiology  Dermatology  Anti-Infectives  Women's Health  Urology  Mental Health  Other:	 Cosmetic  Diabetes  Infectious Disease  Neurology  Oncology  Ophthalmology  Pain Management  Gastrointestinal

31 Oct 17

Sponsor: Guardian Health Sciences, Inc

Protocol #: ~~Lumigear #1~~ JT

Data and Safety Monitoring: A system for appropriate oversight and monitoring of the conduct of the study to ensure the safety of participants and the validity and integrity of the data.
 
6. Data and safety monitoring will be conducted by:
 
 Data Safety Monitoring Board/Committee  Principal Investigator (PI)  Sponsor  Other, please attach a description  None, please attach a rationale
	

7. Is the data and safety monitoring plan identified in the protocol?
 
 Yes, please identify the page #: 4-5  No, please describe your plan for monitoring safety and the integrity of the data:
	

8. Will you ensure the site(s) have the necessary emergency or safety equipment to conduct the study in accordance with the protocol?
 
 No, please explain  Yes  N/A (for minimal risk research only)
	

9. Will the study be posted to the ClinicalTrials.gov website?
 
 Yes  No. If no, please provide a rationale: non significant risk, but will post if requested/required
	

10. Please list all vulnerable populations specifically targeted in this research:
 
 NONE  Children  Children who are wards of State  Pregnant women  Non-English speaking  Adults who do not read and/or write  Patients in nursing homes  Educationally disadvantaged  Economically disadvantaged  Employees or family members of the PI or sponsor  Students of the university or the PI participating in this research  Adults unable to consent for themselves or with diminished decision-making capacity (describe a plan to assess the capacity of these participants to consent/assent).  Other:
	

11. If any vulnerable populations have been identified, please describe the additional safeguards included in the protocol to protect the rights and welfare of these participants:
	

JT 31 Oct 17

Sponsor: Guardian Health Sciences, Inc

Protocol #: Lungeez #1

D. INFORMED CONSENT DOCUMENT INFORMATION:

1.	ICD submitted?	 No (skip to Waiver Requests section)  Yes
2.	Will the protocol allow the sites to use an eConsent process? If yes. This information may be found on page:	 No  Yes
3.	Are there any costs to the participants? Additional costs must be disclosed in the ICD.	 No  Yes (Please describe in an attachment.)
4.	Will a HIPAA Authorization be a part of the ICD?	 No (skip to question 5)  Yes
	If yes, will the authorization include permissions for future research?	 No  Yes (please ensure an explanation is provided in the protocol)
5.	Request for a Waiver of Documentation of ICD?	 No  Yes (Please complete a waiver request)

WAIVER REQUESTS

6.	Request for a Waiver or Alteration of ICD?	 No  Yes (Please complete a waiver request)
7.	Request for a Waiver of HIPAA Authorization?	 No  Yes (Please complete a waiver request)

31 Oct 17 JT

Sponsor: Guardian Health Sciences, Inc

Protocol #: LungscaZ #1

If you are a PM submitting for multi-site research, please complete the following sections.

If single-site, skip to the CERTIFICATION AND SIGNATURE section on the following page.

E. DOCUMENT DISTRIBUTION

Salus IRB is pleased to offer GlobeSync web-portal technology to our clients providing real-time, 24-hour password-protected access to study documents, which will serve as an on-line document repository for study duration. If selected as the distribution method for this research, Salus IRB will distribute all documents via GlobeSync.

Step 1: Please provide a list of names and email addresses of the individuals who are authorized to access study documents. If you require more contacts than the space below allows, please send additional contact information in a separate attachment.

Name	Email Address

Step 2: Each new user must request an account and create a username and password. To request an account:

- go to www.salusirb.com,
- select the GlobeSync button at the top of the screen,
- select "Request an Account", and
- follow the prompts to create your user information.

An email notification is sent to authorized users when study documents are available on GlobeSync. This notification will include a link to the secure site to allow access to the approved documents.

Please note: In order to ensure continued confidentiality of study documents, please notify Salus IRB of any staff changes that require us to disable GlobeSync access.

Please check here if GlobeSync™ is not feasible for you. Please provide an email address in Section A for document distribution.

Per Form 110B JT 31Oct17

F. STUDY MANAGEMENT:

1.	Number of total sites, per the protocol:	
2.	Number of sites to be submitted to Salus IRB:	
3.	Describe your plan to ensure the management of information that might be relevant to the protection of participants is appropriately communicated in a timely manner to the investigative sites and Salus IRB.	
4.	Who will be responsible for submitting study-wide notifications or modifications in the research, such as protocol revisions/amendments, product information updates, unanticipated problems, etc., to Salus IRB?	 Sponsor/Sponsor Representatives  PI(s)

JT 31 Oct 17

Sponsor: Guardian Health Sciences, Inc

Protocol #: 10mgear-#1

If you are a PM submitting for multi-site research, please complete the following sections.

G. RECRUITMENT MATERIAL:

1.	Will the sponsor provide template recruitment material for this research? See the Guidance on Recruitment and Study Material for additional instruction.	 No (skip to section H)  Yes (identify below)
2.	Please forward the Microsoft Word version of each file requiring review. Include the document title and version (number or date) in each file. The following template recruitment material is attached: 
  Proposed printed advertisement, #  Proposed web site content, #  Script of proposed video recording, #  Script of proposed audio recording, #  Participant screening tool (phone screening), #  Other (describe/indicate quantity): 	

H. STUDY MATERIAL:

1.	Will the sponsor provide template study material for this research? See the Guidance on Recruitment and Study Material for additional instruction.	 No (skip to section I)  Yes (identify below)
2.	Please forward the Microsoft Word version of each file requiring review. Include the document title and version (number or date) in each file. The following study material is attached: 
  Participant diaries, #  Survey instrument(s) or questionnaire(s), #  Participant education material, #  Additional material to be distributed to participants (e.g. non cash gifts for long-term retention), #  Other (describe/indicate quantity): 	

I. TRANSLATION REQUESTS:

1.	Will the documents(s) require translation?	 No (skip this section)  Yes
2.	Who will translate these documents?	 Salus IRB (complete #3)  Sponsor or site (skip to next section)
